4. To describe the association of risk factors with performance on neurocognition, behavioral symptoms and MEPs amplitude measure of both groups at 15 treatment sessions (acute phase) and at 4 weeks of maintenance.

RESEARCH STRATEGIES OR METHODS

Methods:

According to the classification of: Alvan Feinstein, this is a clinical trial, single-blind, comparative study (CE + active tDCS vs CE + sham tDCS), randomized, longitudinal and prospective.

The sample size was calculated with the G*Power 3.1 program with an effect size of 0.03 with a formula for factorial ANOVA (between-subjects, within-subjects and interaction effect) with 90%

power, at an alpha of 0.05, with 2 groups and 3 measurements, the final sample would be constituted by a total of 60 participants, which means 30 patients in each analysis group (Jacob Cohen, 1977). The sample will be divided into 2 experimental groups of undergraduates.

1. Group EC + tDCS active = 30
2. Group EC + simulated tDCS =30

Study population:

Selection criteria

Inclusion criteria

1. Age \geq 18 years old.
2. Vaccinated against SARS-COV2 virus.
3. Students of the Faculty of Medicine of UNAM
4. Fluent in Spanish.
5. Adequate visual and auditory acuity to be able to perform neuropsychological tests and cognitive stimulation.
6. Depressive symptoms with working memory impairment (diagnosed by applying a specific neuropsychological battery).
7. That they are not under antidepressant pharmacological treatment prior to entering the investigation.
8. Good general health without medical illnesses (systemic arterial hypertension, diabetes mellitus, dyslipidemias, infections, thyroid disease, vitamin deficiencies) that do not interfere with the study.
9. Willingness to participate in a scheduled 8-week study and able to attend scheduled evaluations.

Exclusion criteria

1. Any neurological disease that allows suspicion of cognitive failure other than depression, such as Parkinson's disease, multiple infarct dementia, Huntington's disease, hydrocephalus, brain tumor, progressive supranuclear palsy, seizure disorder, subdural hematoma, multiple sclerosis, history of head injury with loss of alertness.
2. Participants with a history of severe psychiatric disorders according to DSM-5 (bipolar disorder, schizophrenia, chronic depression) or psychotic features, agitation or behavioral problems in the last three months that could lead to difficulties in complying with the protocol.

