3. History of psychoactive substance abuse and current alcohol consumption with a pattern of abuse or dependence in the last two years.
4. Participants with alterations in a conventional electroencephalogram (paroxysmal phenomena identified by a neurophysiologist).
5. Participants with pacemakers, intracranial metal objects or history of brain surgery, aneurysm clips, artificial heart valves, ear implants, metal fragments or foreign objects in the eyes, skin or body.

Elimination criteria

1. Request to leave the studio.
2. Participants whose clinical condition or laboratory findings require the initiation of complementary treatment with other drugs.

3. The presence of adverse incidents that deteriorate the participant's health (acute confusion, agitation, mania).
4. The presence of exacerbation of neurocognitive or behavioral symptoms during treatment.

Instruments or tools:

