A descriptive analysis of the demographic and clinical characteristics will be performed with frequencies and percentages for the categorical variables and with means and standard deviations for the dimensional variables. Repeated measures ANOVA will be used for the dimensional variables under study. The level of statistical significance was set at a $p \leq 0.05$ for all analyses. Clinical, demographic and baseline variables will be tested for differences between groups with χ^2 or analysis of variance (ANOVA). If any differences between groups emerged ($p < 0.05$), the corresponding variables will be included as covariates in the following analyses.

The groups will be included in a two-measure repeated multivariate analysis of variance (MANOVA) model to examine the direction of changes (time effect) between groups (interaction effect) in terms of the variables to be studied, including cognition, working memory and P300 potentials. A p value of 0.05 will be used as statistically significant for the MANOVA analyses due to the objective of testing the therapeutic efficacy of the intervention.

tDCS+EC reduce Type I error.

Effect sizes of comparisons were estimated using partial eta squared (η^2) and reference values for interpretation of 0.01 = small, 0.06 = medium, 0.14 = large (COHEN, 1988).

All these analyses will be performed using the Statistical Package for the Social Sciences (SPSS), version 22.

ETHICAL CONSIDERATIONS AND/OR LETTER OF INFORMED CONSENT

This project offers a form of therapeutic intervention both by the application of tDCS and the application of the paradigm with TMS, which correspond to a level of risk higher than the minimum according to the regulation of the general health law on research for health, article 17: those in which the probabilities of affecting the subject are significant, among which radiological studies with microwaves and drug trials are considered, due to the fact that brain stimulation interventions approved by the health authorities (e.g. Food and Drug Administration of the USA and COFEPRIS) are carried out for their use in major depression.

The study was planned in accordance with the principles stipulated in the Declaration of Helsinki. The data generated from the research will be used only for scientific purposes without any other use, thus guaranteeing absolute confidentiality of the data obtained from the participants (WMA Declaration of Helsinki, 2013).

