Safety measures will be taken such as ruling out from the beginning the presence of a history of convulsive risk (possible risk in any form of electrical stimulation of the central nervous system), as well as ruling out abnormalities in the excitability of the central nervous system (dysrhythmias, paroxysmal activity, graphoelements suggestive of epileptic activity, etc.), as well as other functional alterations of the central nervous system.

The most commonly reported effects are headache and burning at the application site; however, information will be provided regarding other side effects; in subsequent interviews, the participant will be asked propositional questions regarding possible side effects associated with the use of tDCS or the measurement of P300 cognitive potentials; the participant will also have the telephone numbers to contact the researcher and will be informed about the opening hours of the Continuing Psychiatric Care service of the institution to receive attention in case of any eventuality.

Adverse events that occur in participants will be reported using the format for reporting adverse incidents of medical devices in clinical research, the notification will be made by the principal investigator in accordance with the General Health Law and NOM-240-SSA 1-2012 on the installation and operation of technovigilance following the administrative guide for the integration of the technovigilance report.

With respect to the cognitive stimulation and the clinimetric and neuropsychological measurements to be performed during the protocol, no risk is involved for those who agree to participate in the study. In case of performance anxiety, it will be applied by an experienced clinician who will be with the participants at all times.

Before entering this research project, the participant and his/her family member must read and discuss the informed consent document with the investigator. This document, in turn, must be signed and a copy given to them, while an additional copy will be attached to the research file. Throughout the research, the names of the participants will be omitted from the databases; they will be assigned to a sequential code for statistical analysis.

Participants may withdraw at any time during the course of the research without prejudice to their academic career.

INFRASTRUCTURE

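### The sample size uses the same 60 as the number allocated and the number analysed, with no allowance for loss, so the 90% power claim is supported only if nobody is lost

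*Combined protocol and SAP*

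**What the plan says.** Under RESEARCH STRATEGIES OR METHODS, Methods, the inputs are: "The sample size was calculated with the G*Power 3.1 program with an effect size of 0.03"; a "formula for factorial ANOVA (between-subjects, within-subjects and interaction effect) with 90" per cent; "power, at an alpha of 0.05, with 2 groups and 3 measurements". The result is "the final sample would be constituted by a total of 60 participants, which means 30 patients in each analysis group". The next sentence is "The sample will be divided into 2 experimental groups of undergraduates", and the list below it gives 30 to the active arm and 30 to the sham arm. The number in the calculation, the number allocated and the number in the analysis groups are therefore the same.

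Four elimination criteria follow. They are a request to leave, "Participants whose clinical condition or laboratory findings require the initiation of complementary treatment with other drugs", adverse incidents that harm the participant's health, and worsening symptoms. The fourth refers explicitly to the treatment period, so it operates after randomisation. The ethics section adds: "Participants may withdraw at any time during the course of the research without prejudice to their academic career".

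Statistical analysis says "Repeated measures ANOVA will be used for the dimensional variables under study" and later describes a two-measure repeated MANOVA. No section gives an expected loss rate, a replacement rule, an analysis population or a missing-data rule.

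**The concern.** A power figure applies to the participants who contribute data to the test. When that number is also the number randomised, the plan assumes full retention without saying so. Here the plan itself names routes out of the study. Participants have depressive symptoms and enter without antidepressants, so starting a drug during the study is foreseeable and is one of the elimination criteria. The schedule is demanding: 15 weekday stimulation sessions, 4 weekly maintenance sessions, parallel cognitive stimulation, and assessments at baseline and two later time points.

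If some participants are lost from the analysis, the trial is more likely to miss a real effect than the plan states. A null result could then be read as a negative finding at 90% power when the plan had not supported that figure.

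**Working it through.** **Inputs from the documents.** Two groups, three measurements, alpha 0.05, power 90%, total N = 60, effect size 0.03 with no metric given. The correlation among measures (rho) and any sphericity correction are not stated.

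**Step 1: can 90% at 60 be reproduced?** The test is the group × time interaction in a repeated-measures ANOVA under sphericity, with noncentrality λ = f² × N × m / (1 − rho), m = 3, df1 = 2 and df2 = 2(N − 2). At N = 60, df2 = 116. The values of rho are assumed.

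| Reading of 0.03 | Power at 60, rho 0 to 0.7 | Power at 60, rho 0.5 | N for 90%, rho 0.5 |
|---|---|---|---|
| Cohen's f = 0.03 | about 6% to 9% | 7.5% | 2346 |
| Partial eta squared (f = √(0.03/0.97) = 0.176) | 54% to 97.5% | 84.7% | 70 |
| Misprint for f = 0.3 | 95.4% to above 99.9% | above 99.9% | 26 |

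At rho 0, 0.3, 0.5 and 0.7, none of these readings with three measures gives 60 for the interaction, within-subjects or between-subjects test. The stated figure does not reproduce, so what follows is conditional on the plan's own claim.

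**Step 2: take the claim at face value.** Write λ = c × N and solve for the c that gives power 0.900 at N = 60. The result is c = 0.21645, so λ = 0.21645 × 60 = 12.99. Keep c fixed and lower N. The loss rates are assumptions.

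| Assumed loss | Analysed N | λ = c × N | df2 | Power |
|---|---|---|---|---|
| 0% | 60 | 12.99 | 116 | 90.0% |
| 5% | 57 | 12.34 | 110 | 88.3% |
| 10% | 54 | 11.69 | 104 | 86.4% |
| 13% | 52 | 11.26 | 100 | 85.0% |
| 20% | 48 | 10.39 | 92 | 81.8% |
| 30% | 42 | 9.09 | 80 | 75.8% |

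Losing 8 of 60 (13%) costs 5 points.

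**Step 3: does the choice of test matter?** With one numerator degree of freedom (two measures, or the between-subjects test), df2 = N − 2 and c = 0.18112. Power is 86.6% at 54, 82.3% at 48 and 76.8% at 42, which is the same pattern.

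**Step 4: how sensitive is this to the effect-size reading?** Under f = 0.03, going from 60 to 48 changes power by about 1 point or less, because power is already under 10%. Under f = 0.3, power at 48 is still 89.7% (rho 0) to above 99.9% (rho 0.7). Under partial eta squared with rho 0.5, power falls from 84.7% to 75.2%. The real cost of attrition cannot be fixed until the effect size is.

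**The case against.** The strongest reply is that the plan contains no arithmetic error: 60 divided by 2 is 30. The paragraph speaks of a final sample and of analysis groups, which could mean a target for participants analysed, and silence on replacement does not prove that no one will be replaced. This stands in part. It rules out saying that 30 per group and 90% power will not be delivered. That stronger reading is tempting, but it needs three facts that the documents do not give: that participants are lost, that eliminated participants leave the analysis, and that they are not replaced. It does not remove the point, because the same 60 are expressly divided into the two arms and nothing protects the 30 per analysis group.

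A second reply concerns timing and the model. Elimination criteria 1 to 3 carry no timing, and consent and baseline testing precede randomisation, so some eliminations could come before allocation. A reader might also infer that one missed follow-up visit removes a student from the whole analysis. That presumes a three-measure, complete-case model. The plan also names a two-measure MANOVA, under which a student who missed the other visit could stay in, and it states no missing-data rule. Both remarks stand. Criterion 4 and the right to withdraw at any time still allow loss after randomisation.

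The third reply is that percentages built on 90% at 60 rest on an irreproducible figure. This stands too: they show what the plan's claim implies and do not estimate this trial's power.

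**Conclusion.** The sample-size statement is wrong as written. It equates participants allocated with participants analysed, while other sections provide for loss after randomisation and no allowance or replacement is stated. The 90% claim is supported only with zero loss from the analysis.

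The size depends on two assumptions: that 60 complete cases give exactly 90%, and that the loss rate lies in the range shown. At 5% to 20% loss the cost is about 2 to 8 points (88.3% down to 81.8%). A reader might infer that the trial's true power is 82% to 86%. The documents do not support that, because at the stated 0.03 the power with full retention ranges from under 10% to above 95%, depending on the metric and the correlation. The effect-size problem is the larger fault and comes first, but correcting it alone would still leave a calculation with no allowance for loss.

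**What to change.** Change the sample-size paragraph under Methods, in this order:

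1. Restate the effect size, its metric, the correlation among measures and the test being powered, and recompute.
2. Describe the 60 as randomised, 30 per group, and delete the clause about 30 patients in each analysis group.
3. State an assumed loss rate and the resulting number expected with complete data, for example 60 × 0.90 = 54 or 60 × 0.80 = 48. Say whether eliminated participants are kept in the analysis or replaced, since this number depends on it.
4. Restate power for that number from the corrected inputs. The conditional 82% to 86% above should not be copied in.

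The cost is a few reworded sentences and a recalculation. No extra participants, visits or staff are needed. The downside is that the stated power will be less favourable than the same calculation without loss.

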Cognitive stimulation application

Cognitive stimulation will require a printed manual and will be carried out in groups of 13 participants, three sessions per week for three weeks (acute) and one session per week for four weeks (maintenance). In the following table, the domains to be stimulated are specified, selected from the U.M.A.N. manual.

DOMAINS	SPECIFIC DOMAINS
Orientation	Space Temporary Staff
Memory	Episodic Visual

	Long-term visual Semantics Visual recognition Job
Attention	Sustained Divided
Language	Expressive (oral) Printed (written) Fluency
Praxias	Constructive
Gnosias	Visual Space
Reasoning	Sequencing
Calculation	Mental
Processing speed	Written Visual

Definition of clinical and neuropsychological improvement or response to treatment.

A positive intervention effect will be considered if there is a change or remains the same in the following dimensions of the previously described instruments and scales

- Cognitive:** remain the same or increase by 1 point on the Montreal Cognitive Assessment.
- Behavioral:** no decrease in Lawton & Brody Index and Katz Index values, and 1-point decrease in Cummings Neuropsychiatric Inventory (NPI).
- Neuropsychological:** increase one standard deviation in T-score of the values obtained for each scale.
- Electrophysiological:** increase MEP amplitude from the seventh stimulus onwards * $p>0.05$
- Global:** remain the same or have increased 1 point on the Clinical Global Impression Scale and 1 on the Everyday Life Memory Failure Questionnaire.

General procedure

Students will be recruited through the dissemination of the study at the School of Medicine.

In all cases, they must comply with the safety measures to be able to participate and will be evaluated in an initial interview to ensure that they meet the inclusion criteria. In this interview they will be explained in detail what the study consists of, and if they agree to participate and sign the informed consent letter, a time will be agreed upon for the baseline clinical evaluation. Each of the candidates who meet the selection criteria will be verbally invited to participate in the study after explaining the objectives and procedures of the study.

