Prior to entry into this research project, the participant will have read and discussed the informed consent document with the principal investigator. Those who agree to participate will be asked to review and sign the informed consent form once all questions have been answered. All participants will be assigned a registration number. They will be given a booklet with information on cognitive stimulation and another on neuromodulatory techniques (rTMS and tDCS).

Subsequently, a clinical interview will be conducted to capture relevant demographic and clinical data, and the clinical and neuropsychological instruments will be applied for diagnostic certainty, which

in turn will count as baseline measurement. The total application of the instruments could be done in one session (3 hours with a 15-minute break). After that, the questionnaire of stimulation safety measures will be applied (see APPENDIX) and the recording of P300 potentials will be carried out with the application of the 5 Hz paradigm. The following measurements will be taken at the end of the 15 sessions and at the end of maintenance.

The patient will then be randomly assigned to one of the two tDCS groups and will be given 15 sessions, 5 per week from Monday to Friday and then one per week for 4 weeks. After each session, adverse effects will be asked about and recorded in a questionnaire (see APPENDIX). They will be evaluated at the beginning, at the end of the 15 sessions (three weeks) and four weeks after the end of the study maneuver (the characteristics of each maneuver are described in the methods section corresponding to each stimulation technique). At the same time, all participants will receive three sessions per week of cognitive stimulation using the manual adapted to Mexican Spanish of the UMAM method.

The randomization will be carried out with a list of numbers in Excel that will be in charge of one of the members of the research who will not have contact with the participants.

The applicators of the stimulation techniques will be the same as the assessors and will not remain blind to the maneuver, unlike the students. All applicators will be randomized to form the two groups and the applicator of the techniques will know whether it is the experimental maneuver or the placebo maneuver.

Statistical analysis

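### Participants can be eliminated for worsening after randomization, and the plan does not say whether they are followed, how missing scores are handled, or that everyone is analysed as allocated

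*Combined protocol and SAP*

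**What the plan says.** Besides a request to leave, the Elimination criteria name three grounds:

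- Criterion 2: "Participants whose clinical condition or laboratory findings require the initiation of complementary treatment with other drugs".
- Criterion 3, which begins "The presence of adverse incidents that deteriorate" and refers to the participant's health.
- Criterion 4: "The presence of exacerbation of neurocognitive or behavioral symptoms during treatment".

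General procedure places random allocation before the 15 sessions, so criterion 4 can only act on randomized participants. Criteria 2 and 3 carry no time point, but they are listed apart from the entry criteria.

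On who treats and measures, General procedure says: "The applicators of the stimulation techniques will be the same as the assessors and will not remain blind to the maneuver". On visits it says "The following measurements will be taken at the end of the 15 sessions and at the end of maintenance", and shortly afterwards it places the last evaluation "four weeks after the end of the study maneuver".

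Statistical analysis gives descriptive statistics, repeated-measures ANOVA and a two-measure repeated MANOVA of the groups. The sample-size paragraph in Methods assumes three measurements. Baseline variables become covariates only if the groups differ at p < 0.05. Neither General procedure nor Statistical analysis mentions an analysis set, missing data, or what happens to an eliminated participant's later assessments.

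**The concern.** The objective is to improve working memory and cognitive functioning. A rule that removes people for neurocognitive worsening therefore selects on something close to the outcome. If they also drop out of the analysis, the comparison is no longer between the groups that randomization formed.

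Two features add to this. First, exacerbation has no cut-off and no named decision-maker. The response section defines only improvement: "A positive intervention effect will be considered if there is a change or remains the same in the following dimensions". The test battery is scheduled at three visits, so an elimination between visits would rest on clinical judgement. Second, the people in contact with participants know the allocation, so the threshold could differ between arms.

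At stake is the size, and possibly the sign, of the efficacy estimate in a trial of 30 per arm. A smaller matter is that choosing covariates by a baseline significance test gives up some precision.

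**Working it through.** **Plan's own figure.** There is none on this point: the documents give no elimination rate, outcome SD or between-visit correlation. What follows is an illustration, and every input except 30 per arm is assumed.

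**Model.** Scores at baseline, week 3 and last visit are normal with SD 1 and pairwise correlation ρ = 0.5 or 0.7. Elimination depends on a trigger that correlates r with the week-3 change: r = 1 (follows the score exactly) or r = 0.5. The true effect d is the same at both later visits. The analysis is change from baseline in those retained.

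**Formulas.**

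- SD of change: s = √(2(1−ρ)) = 1.00 at ρ = 0.5 and 0.775 at ρ = 0.7.
- Removing the lowest fraction p of the trigger raises the retained mean week-3 change by r·s·λ(p), with λ(p) = φ(z_p)/(1−p). So λ(0.10) = 0.1755/0.90 = 0.195, λ(0.20) = 0.2800/0.80 = 0.350 and λ(0.30) = 0.3477/0.70 = 0.497.
- The two changes share the baseline: covariance 1−ρ, variance 2(1−ρ), correlation 0.5. The shift at the last visit is half that at week 3.

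**A. True effect 0.5 SD, common threshold, 20% of sham eliminated.** The active rate is Φ(−0.842 − r·0.5/s).

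- r = 1, ρ = 0.5: Φ(−1.342) = 0.090, λ = 0.178. Week 3: 0.5 + 1.00 × (0.178 − 0.350) = 0.33. Last visit: 0.5 − 0.086 = 0.41.
- r = 1, ρ = 0.7: Φ(−1.487) = 0.068, λ = 0.142. Week 3: 0.5 + 0.775 × (0.142 − 0.350) = 0.34. Last visit: 0.42.
- r = 0.5: active rates 0.137 and 0.122, λ = 0.255 and 0.231. Both values of ρ give 0.45 at week 3 and 0.48 at the last visit. If the trigger carried the whole treatment effect instead, these would be 0.41 to 0.42 and 0.46.

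**B. No effect, 30% of active and 10% of sham eliminated.** Bias at week 3 = r·s·(0.497 − 0.195).

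**C. No effect, 20% eliminated in both arms, score-driven in sham only.** Bias at week 3 = −r·s·0.350.

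| Scenario | ρ | r = 1: week 3 / last | r = 0.5: week 3 / last |
|---|---|---|---|
| A, estimate of 0.50 | 0.5 | 0.33 / 0.41 | 0.45 / 0.48 |
| A, estimate of 0.50 | 0.7 | 0.34 / 0.42 | 0.45 / 0.48 |
| B, bias | 0.5 | 0.30 / 0.15 | 0.15 / 0.08 |
| B, bias | 0.7 | 0.23 / 0.12 | 0.12 / 0.06 |
| C, bias | 0.5 | −0.35 / −0.17 | −0.17 / −0.09 |
| C, bias | 0.7 | −0.27 / −0.14 | −0.14 / −0.07 |

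Swapping the rates in B reverses the sign. If rates and reasons are the same in both arms and there is no effect, the bias is zero.

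**Type I error.** Simulation of 30 per arm agrees with these means to about 0.01 SD. In scenario B the two-sided 5% test of change rejects in about 24 to 25% of trials at week 3 and 8% at the last visit for r = 1. For r = 0.5 the figures are about 8% and 5 to 6%.

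**Covariate rule.** Simulated power for 0.5 SD at the last visit, always adjusting for baseline, is 59%, 75% and 88% at ρ = 0.5, 0.7 and 0.8. The three-measure group-by-time test gives 49%, 73% and 89%. The gain is real at moderate correlation and absent at high correlation.

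**The case against.** The strongest reply is that the text nowhere says eliminated participants leave the analysis. Elimination could mean only that stimulation stops. Consent pages and appendices are also not in the available text, so a follow-up rule might exist elsewhere. This stands in part: exclusion is an inference from the default behaviour of the named methods. But the statistical section is present and silent, and a plan should not leave this to software defaults.

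A second reply is that elimination may be rare. The entry criteria exclude severe psychiatric disorders, and the background calls side effects generally mild. That stands as to size, and the documents cannot settle it.

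A third is that safety is recorded throughout: "After each session, adverse effects will be asked about and recorded in a questionnaire". The ethics section adds later interviews and formal incident reports. So worsening would not go unrecorded. These are safety records, however, and do not supply the missing cognitive and P300 scores.

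A reader might also infer that unblinded staff will produce a false benefit for active stimulation. The documents do not support that. They do not say who decides on elimination, and scenarios A and C run against active stimulation. Nor may one infer the reverse, that equal rates make the problem harmless: scenario C shows that the reasons must match as well.

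Finally, the covariate rule might be read as invalidating the tests. Repeated-measures ANOVA already uses the outcome's baseline as a time point, and the case here rests only on lost precision.

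**Conclusion.** The gap is established: there are elimination rules tied to the outcome domain, and no stated analysis set, follow-up of eliminated participants or missing-data method. That it will lead to a completer analysis is likely but inferred.

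The direction of bias is open. With a real effect and a common threshold it is toward zero. With unequal rates or reasons it can favour either arm. It vanishes under no effect only if both rates and reasons are equal.

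The size is unknown. The figures above are neither bounds nor forecasts. They rest on normal scores, elimination driven by the week-3 change, and assumed rates and correlations. They show that the bias can be material if elimination tracks the score closely, especially at week 3, and is modest if the link is loose. Scores lost through elimination cannot be recovered later, so this should be settled in advance. The covariate rule is minor.

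**What to change.** 1. Leave the rules for stopping stimulation as they are, but separate stopping stimulation from leaving the trial. Keep assessing every consenting participant at the two post-baseline visits already scheduled. First reconcile the two descriptions of the last visit. They coincide at week 7 (3 + 4) if the maneuver means the 15 sessions. They differ if it includes maintenance (3 + 4 + 4 = week 11), while the Inclusion criteria describe an 8-week study.
2. Analyse all randomized participants as allocated in a mixed model of the post-baseline scores, with group, visit, group by visit, and the outcome's baseline score wherever one is collected. None is described for academic performance. State which visits are analysed, since two and three measures both appear.
3. Drop baseline significance tests as the way to choose covariates.
4. Report eliminations by arm with reason and timing. Keep the completer ANOVA as secondary. Add one sensitivity analysis that shifts missing scores, for example by 0 to −0.5 SD in either arm, and shows where the conclusion changes.

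Step 1 matters most. In scenario B at the last visit, a baseline-adjusted model with nobody followed still leaves a bias of 0.08 to 0.09 SD (r = 1) or about 0.04 SD (r = 0.5). Following a random half of those who stop brings it to 0.01 to 0.03 SD.

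The cost is SAP wording, a mixed-model procedure in the SPSS package already named, and slightly more follow-up and analysis work. The Inclusion criteria already ask for attendance at scheduled evaluations. The estimate will then describe assignment to treatment, including those who stopped. That answers a different question from the effect in completers, and the report should say so. Participants who withdraw consent cannot be followed.
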